a-MCI	Amnestic Mild Cognitive Impairment
ANCOVA	Analysis of Covariance
a-PET	Amyloid Positron Emission Tomography
ARIA	Amyloid Imaging Related Abnormalities
ARIA-E	ARIA-vasogenic edema and/or sulcal effusion
ARIA-H	ARIA-micro-hemorrhage
ATC	Anatomical Therapeutic Chemical
BADL	Basic Activities of Daily Living
BMI	Body Mass Index
CDR	Clinical Dementia Rating scale
CI	Confidence Interval
CS	Clinically Significant
CSF	Cerebrospinal Fluid
CSR	Clinical Study Report
C-SSRS	Columbia Suicide Severity Rating Scale
DBL	Database Lock
DSMB	Data Safety Monitoring Board
ECG	Electrocardiogram
ELISA	Enzyme-linked Immunosorbent Assay
EQ-5D-5L	EuroQol 5 dimensions
IADL	Instrumental Activities of Daily Living
ICH	International Conference on Harmonisation
IGE	Investigator Global Evaluation
ITT	Intent-to-Treat
KLH	Keyhole limpet hemocyanin
LS	Least Squares
MedDRA	Medical Dictionary for Regulatory Activities
MCI	Mild Cognitive Impairment
mITT	Modified Intent-to-Treat
MMSE	Mini Mental State Examination
MMRM	Mixed-Model Repeated Measures
MRI	Magnetic Resonance Imaging

Abbreviation	Description
NCS	Not Clinically Significant
OD	Optical Density
PP	Per Protocol
PT	Preferred Term
Q1	First Quartile
Q3	Third Quartile
RBANS	Repeatable Battery of the Assessment of Neuropsychological Status
SAESI	Serious Adverse Event of Special Interest
SAP	Statistical Analysis Plan
SB	Sum of Boxes
SD	Standard Deviation
SI	Severity Index
SOC	System Organ Class
TEAE	Treatment-Emergent Adverse Event
TESAE	Treatment-Emergent Serious Adverse Event
TMT	Trail Making Test
VAS	Visual Analogue Scale
VM-AD	Very Mild Alzheimer's Disease
WHO-DD	World Health Organization Drug classification Dictionary

1 INTRODUCTION

This SAP is addendum 02 to SAP version 1.0, 25Nov2021. Due to the extent of changes required to SAP version 1.0 and addendum 01 to SAP version 1.0, it was decided that the details of the planned statistical analyses for the study would be clearer if the SAP was rewritten and presented as a stand-alone document addendum 02 to SAP Version 1.0.

1.1 Purpose and Scope of Analysis Plan

The purpose of this statistical analysis plan (SAP) is to provide detailed information to aid in the implementation of the statistical analysis of the study data. It briefly summarizes the protocol, describes the analysis sets that will be analyzed, and describes the analyses to be performed. The details of the specific statistical methods that will be used are provided. Post database lock (DBL), it may become apparent that the planned analyses should be modified, e.g., modeling assumptions are untenable. Any modification to the original analysis plan will be identified and described in the clinical study report (CSR).

Table, figure, and listing specifications are in separate documents. This analysis plan is meant to supplement the study protocol. If differences occur between analyses described in the SAP and the current protocol, those found in this SAP will assume primacy.

This SAP is written with due consideration of the recommendations outlined in the most recent International Conference on Harmonisation (ICH) E9 Guideline entitled Guidance for Industry: Statistical Principles for Clinical Trials and the most recent ICH E3 Guideline, entitled Guidance for Industry: Structure and Content of Clinical Study Reports and will be finalized prior to DBL.

1.2 Study Rationale

The purpose of this Phase II study is to confirm in patients with amnestic mild cognitive impairment (a-MCI) or very mild Alzheimer's Disease (vm-AD) the level of safety and tolerability obtained in the ABvac40 Phase I clinical trial (a randomized, placebo-controlled, parallel group, double-blinded, single-center, phase I pilot study to assess tolerability and safety of repeated subcutaneous administration of two single-doses of ABvac40 applied to patients with mild to moderate Alzheimer's disease – AB1203 Study). In addition, the study is aimed to better characterize the immune response elicited by ABvac40 and to explore its effects on Alzheimer's Disease (AD) biomarkers.

2 PROTOCOL SUMMARY

2.1 Study Design

[figure not shown]
This is a multi-center, prospective, longitudinal, randomized, double-blind, placebo-controlled, two parallel treatment groups (ABvac40 and placebo), confirmatory phase 2 clinical trial, designed in two parts: Part A, to evaluate repeated subcutaneous injections of ABvac40 to determine the safety, tolerability, and immune response in patients with amnestic mild cognitive impairment (a-MCI) or very mild Alzheimer's disease (vm-AD). Part B, to assess the safety, tolerability and efficacy of a delayed-start vaccination, and the long-term safety and tolerability of ABvac40 in patients receiving a booster after their Part A vaccination scheme.

2.1.1 Part A

Part A of the study will last for up to 24 months (from V0 to V25) and at least 18 months (up to V23) during which randomized study participants will receive five monthly (every four weeks) immunizations plus a booster shot at month 10 (V18). During the study, two interim analyses will be performed to assess safety, tolerability and biological activity of the treatment (including data from the collected disease biomarkers). These analyses will be reviewed by an independent Data Safety Monitoring Board (DSMB).

Additionally, after all patients complete their 18-month visit (V23) of Part A, a statistical analysis will be performed to determine whether Part B of the study should be discontinued. The study scheme for Part A is shown in Figure 1.

Figure 1: AB1601 Study Schematic – Part A

[figure not shown]

2.1.2 Part B

Part B of the study will last for 18 months (from V1B to V22B). The scheme of visits will mirror the Part A scheme. The first visit of Part B (V1B) will take place at least 18 months after the patient started Part A (i.e., patient should have completed V23 which is month 18 of Part A to enter Part B). The study scheme for Part B is shown in also included in Figure 2.

The patients randomized to the placebo group during Part A will receive five monthly (every four weeks) immunizations with ABvac40 plus a booster shot after 6 months (Placebo arm Part A / ABvac40 arm Part B), whereas the patients randomized to the ABvac40 group during Part A will receive placebo following this schedule, except in V13B (Week 16), where they will receive an ABvac40 booster shot (ABvac40 arm Part A / Placebo+Booster arm Part B). Given the extended inclusion period of Part A, the V13B booster will take place at different timepoints relative to the patients' last immunization.

Figure 2: AB1601 Study Schematic – Part B

2.2 Study Objectives

2.2.1 Part A (Randomized, Double-blind, Placebo-controlled – 18 to 24 months follow-up)

2.2.1.1 Primary Safety Objective

The primary safety objective of the study is to evaluate the safety and tolerability of repeated doses of ABvac40 in a population of patients with a-MCI or vm-AD.

2.2.1.2 Primary Efficacy Objective (Immunogenicity)

The primary efficacy objective (immunogenicity) of the study is to assess the immune response produced during the study by repeated doses of ABvac40 in a population of a-MCI or vm-AD.

2.2.1.3 Secondary (Exploratory) Efficacy Objectives

The secondary (exploratory) efficacy objectives of the study are:

- Characterizing the immune response elicited by repeated doses of ABvac40 in a population of a-MCI or vm-AD.
- Assessment of the changes in the disease biomarkers elicited by ABvac40 in the overall study population.
- Assessment of the changes in cognition and quality of life elicited by ABvac40 in the overall study population.

2.2.2 Part B (ABvac40 Delayed Start, Open Label [Part A assignment will remain blinded for investigators and patients] – 18 months follow-up)

2.2.2.1 Exploratory Safety Objective

- To evaluate the safety and tolerability of repeated doses of ABvac40 after delayed start in patients receiving placebo during Part A, and the long-term safety and tolerability of ABvac40 in patients receiving a booster after their Part A vaccination scheme.

2.2.2.2 Exploratory Efficacy Objective (Immunogenicity)

- To assess the immune response produced by repeated doses of ABvac40 after delayed start in patients receiving placebo during Part A.
- To assess the immune response triggered by a second ABvac40 booster in patients receiving ABvac40 during Part A.

2.2.2.3 Exploratory Efficacy Objective (Other)

- To assess the changes in the disease biomarkers elicited by ABvac40 in the overall study population.
- To assess the changes in cognition and quality of life elicited by ABvac40 in the overall study population and according to the treatment scheme during Part A and B.
- To assess the immunological memory, characterizing the immune response ex vivo elicited by the booster in patients who have received ABvac40 during Part A
- To assess the potential relationship between antibody titration, biomarkers and cognitive state.
- To define the optimal ABvac40 treatment scheme.

2.3 Study Population

Patients (between 55-80 years of age) diagnosed either with a-MCI or vm-AD will be included in the trial. To ensure sufficient precision for the primary safety and efficacy endpoints of the study a minimum of 60 patients with a-MCI or vm-AD per treatment group (ABvac40 and placebo) are required. The amyloid Positron Emission Tomography (a-PET) positive and a-PET negative patients will be independently randomized following a 1:1 ratio between ABvac40 and placebo (Part A).

Participants in Part A will have to complete at least their 18-month visit (V23) to be eligible for Part B of the study.

All patients who have participated in Part A who have not experienced any drug reaction and have no Magnetic Resonance Imaging (MRI) safety findings before the first immunization in Part B, may participate in Part B. On completion of Part A of the study, the database containing Part A data will undergo DBL prior to reporting of Part A results. Additionally, Part A and B data will undergo DBL prior to reporting of Part B results.

3 GENERAL STATISTICAL CONSIDERATIONS AND REPORTING CONVENTIONS

The following general analysis and reporting conventions will be used:

- The following treatment labels will be used for presentation of results in the statistical tables:
 - Statistical testing of primary and secondary efficacy outcomes in Part A of the study and summaries of Adverse Events (AE)s across parts A and B of the study will be presented by the following treatment groups:
 - ABvac40
 - Placebo
 - Summary statistics for all other parameters (Part A and Part B, combined) will be presented by the following treatment sequences:
 - ABvac40 arm Part A / Placebo+Booster arm Part B
 - Placebo arm Part A / ABvac40 arm Part B
- Visits will be presented in outputs in terms of weeks, with a suffix of “A” or “B” to indicate the study part (e.g. Week 0A, Week 2A..... Week 0B, Week 2B, etc...).
- Only available data will be included in summary statistics and no substitutions or imputations of missing values will be performed.
- Categorical variables will be summarized using counts (n) and percentages (%) and will be presented in the form n (%). Percentages will not be presented for counts of 0, while percentages of 100 will be reported as a whole number (i.e. “100%”). All other percentages will be presented to 1 decimal place. To ensure completeness, summaries for categorical variables will include all categories, even if no patients had a response in a particular category. Denominators will include patients with non-missing data, unless otherwise specified. The number of patients with missing data for categorical variables will be summarized without a percentage.
- Continuous variables will be summarized using mean, 95% confidence interval (CI) for mean, standard deviation (SD), first quartile (Q1), third quartile (Q3), minimum, maximum, median, and number of patients. The mean, median, Q1, Q3 and CI will be rounded and reported to 1 more level of precision than the original observations, and the SD will be rounded and reported to 2 more levels of precision than the original observations. The minimum and maximum will be reported to the same precision as the original data.
- Following SAS default rules, the median will be reported as the rounded average of the two middle sorted values if the dataset contains even numbers of non-missing data.

- P-values will be rounded and reported to 4 decimal places if greater than or equal to 0.0001. If the rounded p-value is less than 0.0001, '<0.0001' will be reported. If the rounded p-value is greater than 0.9999, '>0.9999' will be reported.
- Unless otherwise specified, the baseline value for all measures will be the last non-missing value recorded prior to the first dose of study treatment. For measurements that occur on the date of the first dose of study treatment with time collected, the measurement will be considered the baseline value if the measurement time is prior to the time of the first dose.
- No preliminary rounding will be performed; rounding will only occur after analysis. To round, consider digit to right of last significant digit: if < 5 then round down, if ≥ 5 then round up.
- All listings will be sorted in order of patient, parameter (when applicable), and time of assessment (e.g., visit, time, and/or event).
- Dates in listings will be displayed as YYYY-MM-DD (e.g., 2022-12-01).
- Where relevant, each listing will present Study Days which will be numbered relative to the initiation of study treatment administration.
 - The start of treatment (Day 1) for Part A is defined as the date in which a patient receives the first study treatment in Part A. The start of treatment (Day 1) for Part B is defined as the date in which a patient receives the first study treatment in Part B.
 - Day -1 is defined as the day before the first administration of study treatment within study Part (A or B). There is no Study Day 0.
 - Negative Study Days occur prior to initial administration of study treatment. Positive Study Days occur the day of initiating study treatment and thereafter.

All dates presented in listing will be accompanied by study day.

- The following details will be footnoted in each table, listing and figure output: program name, programmer name, date of creation of output. Each table and figure will include a footnote referencing the corresponding listing and table number, respectively.
- All analyses will be performed using SAS System version 9.4.

3.1 Analysis Sets

3.1.1 Intent-to-Treat (ITT) Analysis Set

The ITT Analysis Set will include all randomized patients who received any study treatment.

Analysis of all secondary efficacy endpoints will be carried out using the ITT Analysis Set. Patients will be analyzed according to their randomized treatment assignment, regardless of the treatment received.

3.1.2 Modified Intent-to-Treat (mITT) Analysis Set

The mITT Analysis Set will comprise of all patients in the ITT Analysis Set who have a baseline and at least one post-baseline anti-A β 40 antibody assessment (Optical Density (OD) in enzyme-linked immunosorbent assay (ELISA) without pre-adsorption).

Analysis of the primary efficacy endpoint will be carried out using the mITT Analysis Set. Patients will be analyzed according to their randomized treatment assignment, regardless of the treatment received.

3.1.3 Per Protocol (PP) Analysis Set

The Part A PP Analysis Set will comprise of all patients in the ITT Analysis Set who received all doses of study medication (on V1, V4, V7, V10, V13 and V18 in Part A), have attended the safety visit after booster (V20 in Part A), and have no major protocol deviations that could affect the efficacy analyses.

Analysis of the primary efficacy endpoint and secondary efficacy endpoints relating to the characterization of immune response and the assessment of disease biomarkers in Part A will be repeated using the Part A PP Analysis Set.

The Part B PP Analysis Set will comprise of all patients in the ITT Analysis Set who received all doses of study medication (on V1B, V4B, V7B, V10B, V13B and V18B in Part B), have attended the safety visit after booster (V20B in Part B), and have no major protocol deviations that could affect the summary of efficacy.

During the blind review meeting, decisions will be made regarding the PP Analysis Set in terms of whether deviations in Part A affect Part B for inclusion in analysis set.

Summaries of the primary efficacy endpoint and secondary efficacy endpoints relating to the characterization of immune response and the assessment of disease biomarkers over the entire duration of the study (Parts A and B combined), will be repeated using patients who are in Part A PP Analysis Set and the Part B PP Analysis Set.

Patients will be analyzed according to their randomized treatment assignment, regardless of the treatment received.

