22. Participation in another clinical trial within the previous 1 month to screening visit, or within the previous 12 months after the last dose to the screening visit in the case of subjects who participated in trials with a study drug whose intention was to modify the progression AD unless documentation of receipt of placebo is available. The patient cannot be included in the study if the experimental drug was an immunotherapeutic drug, including IVIG or a vaccine against Alzheimer's disease unless documentation of receipt of placebo is available.
23. Patients with alcohol or drug abuse or dependence.
24. Absolute (having a pacemaker or implantable defibrillator) or relative (bare metal stent or stent implanted in the last six months) contraindications to MRI examination. Feeling of claustrophobic do not let perform MRI or PET scan.

25. Patients unlikely to comply with the protocol (e.g., unable to return for follow-up visits).
26. Women of childbearing potential, pregnant or nursing. Note: All women will be considered to be of childbearing potential unless they are postmenopausal (amenorrheic for at least 12 consecutive months, in the appropriate age group, and without other known or suspected cause) or have been sterilized surgically (i.e. bilateral tubal ligation, total hysterectomy, or bilateral oophorectomy, all with surgery at least 1 month before dosing)
27. Significant alterations in the EKG that are associated with an added risk for the patient.

Investigational Product, Dose and Mode of Administration

Study Medication

Name: ABvac40

Active ingredient: Conjugated A β x-40 to KLH

Transporter: Phosphate buffer containing 0.35% aluminium hydroxide (adjuvant)

Pharmaceutical Form: Injection ready vials

Posology: Part A: Verum group: Six administrations: the first five administered once every 4 weeks (28 \pm 3 days) and the sixth at week 42 (V18), 26 weeks after the fifth immunization. Each administration consists of 1mL injection of ABvac40 (containing 0.2 mg of Abetax-40).

Part B: Delayed start group: Six administrations: the first five administered once every 4 weeks (28 \pm 3 days) and the sixth at week 42 (V18B), 26 weeks after the fifth immunization.

Booster group: One administration at week 16 (V13B).

Each administration consists of 1mL injection of ABvac40 (containing 0.2 mg of Abetax-40).

Method of administration: Subcutaneous injection.

Duration of Treatment:

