The participation in the study for each patient will last between 36 and 42 months (Part A + Part B). They will be exposed to the study's drug for an initial period of 16 weeks (V1 to V13 [Part A – Verum group] or V1B to V13B [Part B – Delayed start group]). After 6 months, they will receive the 6th vaccination (V18/V18B). Only the patients assigned to the Verum group in Part A will receive a 7th vaccination at V13B.

Reference Therapy, Dose and Mode of Administration

Comparator

Name: Placebo

Active ingredient: None

Transporter: Phosphate buffer containing 0.35% aluminium hydroxide (adjuvant)

Pharmaceutical Form: Injection ready vials

Posology: Part A: Placebo group: Six administrations: the first five administered once every 4 weeks (28 \pm 3 days) and the sixth at week 42 (V18), 26 weeks after the fifth. Each administration consists of 1mL injection of ABvac40 vehicle.

Part B: Booster group: Five administrations: the first four administered once every 4 weeks (28±3 days) and the fifth at week 42 (V18B), 30 weeks after the forth. Each administration consists of 1mL injection of ABvac40 vehicle.

Method of administration: Subcutaneous injection.

Key Study Variables:*Part A:*Primary Safety Variable:

The rate (%) of Adverse Events (AEs).

Primary Efficacy Variable:

Maximal increment of specific anti-A β 40 antibody signal (antibody titers estimated by ELISA (signal optical density (OD) values) in each subject with regard to the pre-treatment visit (either V0 or V1)

Secondary Safety Variables:

Other secondary safety endpoints will be evaluated, including:

- withdrawal criteria (continuation decision)
- number of withdrawn patients due to adverse events (AEs); cause of withdrawal
- serious adverse events (SAEs)
- physical and neurological examination
- concomitant medication
- vital signs (blood pressure, heart rate, respiratory rate, body temperature), body mass (weight, height).
- brain MRI
- electrocardiogram (EKG)
- analytical haematology, toxicology (reactive protein), biochemistry, coagulation, serology and urine test strip results.

Secondary Efficacy Variables:

- Characterization of the immune response:
 - o Levels of anti-KLH and anti-A β 42 antibodies in plasma
 - o Level of anti-A β 40 antibodies in CSF
 - o Levels of cytokines in plasma including IL-2, IL-4, IL-5, IL-6, IL-10, IL-13, IL-15, TNF- α and IFN- γ .
 - o Analysis of the peripheral blood cell subsets by immunophenotyping.

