2.4.1 Administration of Investigational Products

ABvac40 is administered by subcutaneous injection which proved to be well tolerated in previous pre-clinical and clinical trials. For this Phase II study, five monthly (every four weeks) single-dose injections plus a 6 months (26 weeks) delayed booster of verum (or placebo, as corresponds) are planned for the Part A.

For the Part B, patients receiving placebo in Part A will cross-over to receive verum following the aforementioned scheme (Delayed start group), whereas patients receiving verum in Part A will receive placebo following the same scheme (except in V13B when they will receive a booster of verum) aiming to maintain the blinding for both patients and investigators (Booster group).

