6.1.1.2 Part B

All patients must be tested for COVID-19 during the Part B vaccination visits before receiving their study medication, unless the patient has already overcome the disease (it has to be documented) and remains asymptomatic.

At each vaccination visit, the patients will perform a rapid serological test at the study site to detect SARS-CoV-2 antibodies in serum.

In case the patient test positive and he or she is completely asymptomatic for COVID-19, he will continue with the study normally.

In case the patient test negative, a PCR test for COVID-19 detection will be performed. The required samples will be taken by a trained study staff or delegate and sent to the central laboratory (██████████) where a standard PCR test for COVID-19 detection will be performed.

After 24-48h, the patient will be communicated with the results. In case the patient test negative and remains completely asymptomatic for COVID-19, he or she will continue with the study procedures (including receiving the study treatment) normally.

In case the patient test positive for COVID-19, the PCR test will be repeated until the patient test negative and is asymptomatic. During this time, the patient will not receive the study treatment. The administration of the study treatment can be delayed for up to one month. In case it should be delayed beyond one month, the vaccination will be skipped. Under any delay scenario, the subsequent visits will be re-scheduled accordingly.

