9.7 Subject Population(s) for Analysis

The Safety population consists of all subjects who received any amount of study drug.

The Intent-to-treat (ITT) population consists of all subjects randomized who received at least one dose of study medication for whom at least one post-baseline anti-A β 40 antibody signal assessment is available.

There will be two per-protocol (PP) populations:

- Part A: consists of all subjects who have received all doses of study medication (on V1, V4, V7, V10, V13 and V18), have attended the safety visit after booster (V20) and have no major protocol deviations.
- Part B: consist of all subjects who have received all doses of study medication (on V1B, V4B, V7B, V10B, V13B and V18B), have attended the safety visit after booster (V20B) and have no major protocol deviations.

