7.1 Study Treatment Compliance

Percentage compliance to study drug administration will be calculated as:

% Compliance = (Number of doses of study drug taken in Part A * 100) / 6, rounded to 1 decimal place, where 6 = number of planned doses for Part A

% Compliance = (Number of doses of study drug taken in Part B * 100) / 6, rounded to 1 decimal place,

where 6 = number of planned doses for Part B

Compliance will further be categorized into the following groups: (<80%, \geq 80% to 100%).

Summaries of the calculated compliance and the categorized compliance will be presented by treatment sequence and study part. The denominator for the percent of patients within each compliance category will be the number of patients in the safety analysis set who entered the specific study part. A listing of study treatment compliance will also be presented.

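### The Part B per-protocol rule and compliance score do not fit the Booster sequence, whose only ABvac40 dose is at V13B

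*SAP*

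**What the plan says.** SAP 2.1.2 describes the two Part B sequences. Patients on placebo in Part A get ABvac40 at all six vaccination visits. Patients on ABvac40 in Part A "will receive placebo following this schedule, except in V13B (Week 16), where they will receive an ABvac40 booster shot". The posology text in the Protocol synopsis and section 4.4.1 agrees. For ABvac40 it gives "Booster group: One administration at week 16 (V13B"; for placebo, "Booster group: Five administrations: the first four administered once every 4 weeks (28±3 days) and the fifth at week 42 (V18B". Protocol 2.4.1 states why these patients get placebo: "aiming to maintain the blinding for both patients and investigators (Booster group".

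SAP 3.1.3 sets the Part B PP rule without reference to sequence. It asks for every dose at V1B, V4B, V7B, V10B, V13B and V18B and no major deviation affecting efficacy, and patients must "have attended the safety visit after booster (V20B in Part B". SAP 3.1.4 uses the same dose and visit conditions for PPc. Protocol 9.7 has the same rule: "have attended the safety visit after booster (V20B) and have no major protocol deviations". The combined Part A and B repeats take patients who belong to both the Part A and the Part B set.

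SAP 7.1 defines "Compliance = (Number of doses of study drug taken in Part B * 100) / 6", splits the result at 80%, and makes no distinction between ABvac40 and placebo injections.

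Protocol 6.1.1.2 gives one route by which a Part B dose can be missed. Dosing waits while a patient is COVID-19 positive: "In case it should be delayed beyond one month, the vaccination will be skipped".

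**The concern.** Calling V20B the visit after the booster is correct only for the Delayed-start sequence. In the Booster sequence that visit follows a placebo injection, and the visit that follows the booster, V15B, does not appear in the rule.

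The rule therefore has two faults for that sequence. It removes patients who had the booster and whose post-booster blood was drawn, because a blinding injection or a later visit was missed. It also does not ask for the first post-booster visit. The compliance score has a related fault: it cannot show whether the one ABvac40 dose was given.

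At stake is how well the PP repeats and the compliance table serve the exploratory objective in SAP 2.2.2.2, the immune response to a second booster in patients vaccinated in Part A.

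**Working it through.** **Timing, from the Part B schedule in the Protocol synopsis.** A safety visit falls two weeks after each vaccination.

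- V13B is week 16 and V15B is week 18, so V15B is the visit after the booster: 18 − 16 = 2 weeks.
- V18B is week 42 and V20B is week 44, so V20B is the visit after V18B: 44 − 42 = 2 weeks. V18B is placebo in this sequence.
- Protocol 7.2.1.1 has immune-response blood drawn at V15B, V16B (week 24) and V17B (week 40), all before V18B. A boosted patient can thus have samples up to 40 − 16 = 24 weeks after the booster and still leave the PP set for missing V18B or V20B. A missed injection at week 42 cannot alter results from weeks 18 to 40.

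**The plan's own denominator.** Booster sequence: 1 ABvac40 + 5 placebo = 6. Delayed start: 6 ABvac40 = 6. The 6 in SAP 7.1 reproduces for both.

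**Scores in the Booster sequence**, as 100 × doses / 6:

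| V13B booster | Placebo given (of 5) | Score | Band | Meets PP dose rule | ABvac40 doses in Part B |
|---|---|---|---|---|---|
| Given | 5 | 6/6 = 100% | at least 80% | Yes | 1 |
| Given | 4 | 5/6 = 83.3% | at least 80% | No | 1 |
| Missed | 5 | 5/6 = 83.3% | at least 80% | No | 0 |
| Given | 3 | 4/6 = 66.7% | below 80% | No | 1 |

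Rows 2 and 3 have the same score but differ on the one dose that matters for the booster question. Row 4 had the booster but falls in the lower band; row 3 did not and is in the upper band.

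**Illustrative size of the PP loss.** The documents give no miss rate, so a per-injection probability q is assumed, independent across visits. The share of boosted patients failing the dose rule on placebo alone is 1 − (1 − q)^5. The last column multiplies by 35, the expected completers per arm in Protocol 9.2, and assumes that all of them enter Part B and are boosted.

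| q | 1 − (1 − q)^5 | Of 35 |
|---|---|---|
| 1% | 4.9% | 1.7 |
| 2% | 9.6% | 3.4 |
| 5% | 22.6% | 7.9 |
| 10% | 41.0% | 14.3 |

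The share missing the booster itself would be q. Losses from missing V20B alone are not counted.

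**The case against.** The strongest defence is that a PP set measures adherence to the schedule, and the schedule is six injections for everyone. One rule keeps selection symmetric between sequences shown side by side, and it can be applied at the blind review meeting without knowing the sequence. This is a fair reason to count all injections as adherence to the blinded schedule. It does not make V20B the post-booster visit, and it does not make the count a measure of exposure to the booster.

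The blind review does not solve the problem. SAP 3.1.3 and 3.4 let the meetings judge deviations, including whether Part A deviations carry over to Part B. Nothing there waives the six-dose or V20B conditions.

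The harm from not checking V15B is modest. Summaries are by visit, use available data only and show the number of patients (SAP 3 and 6.2), so a patient without V15B adds nothing at that visit. V16B, V17B and V20B also give post-booster samples, and a missed V15B can be assessed as a deviation. This largely stands.

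Exposure can be recovered elsewhere. SAP 5.1 counts patients who received all immunizations in each part, SAP 7.1 adds a compliance listing, and the adverse event rules in SAP 7.2.1 treat the booster separately. This limits the damage, but the compliance table itself remains uninformative for this sequence.

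The miss rates are assumed and independence is doubtful. Early stopping removes later doses together. A skip under the COVID-19 rule needs a delay beyond one month, and patients who are asymptomatic after documented recovery are exempt from testing. The percentages show scale and are not forecasts.

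**Conclusion.** The point holds, with limited impact. One Part B PP/PPc rule is applied to two sequences and fits only one. In the Booster sequence it drops boosted patients who miss any of five placebo injections or V20B, and it leaves the first post-booster visit unchecked. The compliance score gives 83.3% both to a patient who missed only the booster and to one who missed a single placebo injection.

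Three stronger readings are not supported:

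- **Boosted patients in general are excluded.** A patient with all six injections, V20B attended and no major deviation stays in.
- **A patient who missed the booster passes as per protocol.** The PP rule requires V13B and excludes that patient. Only the compliance table puts the patient in the upper band, and the SAP does not label that band compliant.
- **The booster objective rests on the PP set.** SAP 6.2 gives the combined summaries on mITT (primary endpoint) and ITT (secondary endpoints), which do not require complete dosing. The PP and PPc results are repeats.

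Protocol 4.1.2 says that no hypothesis is tested in Part B, and the Part A confirmatory test is untouched. The scores follow from the documents alone. The number of patients lost depends on the assumed miss rate: 4.9% to 41.0% of boosted patients for rates of 1% to 10%.

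**What to change.** Change analysis definitions only; the dosing schedule is not in question.

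- **SAP 3.1.3, Booster sequence:** ABvac40 received at V13B, V15B attended with an anti-Aβ40 sample, and no major deviation. **Delayed start:** keep the six-dose and V20B rule.
- **SAP 3.1.4 (PPc):** use the same sequence-specific dose and visit conditions and keep the existing deviation conditions, but do not require an antibody sample. SAP 9.2 took that requirement out of ITT so that valid secondary data would not depend on primary-endpoint samples; PPc should not bring it back.
- **SAP 7.1:** report ABvac40 doses (out of 1 for the Booster sequence, out of 6 for Delayed start) separately from placebo injections.
- **Blind review:** flag every patient under both rules before unblinding, then select the applicable flag by program.
- **SAP 9.2:** record the departure from Protocol 9.7. SAP 1.1 already gives the SAP precedence.

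The cost is SAP wording and a few lines of programming. The downside is that PP means different things in the two sequences shown side by side, which is acceptable in a descriptive summary if it is footnoted.
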